#### 9.8. Reporting urgent safety measures

The Sponsor, CI, co-lead, PI, DMC and/or TSC may take appropriate urgent safety measures (USM) in order to protect the participants of a clinical trial against any immediate hazard to their health or safety.

If a PI implements a USM at a site, they must inform the CI immediately (see contact details in key trial contacts section and copy ExeCTU; [contact]). If time permits, the investigator should discuss any proposed actions with the CI prior to implementation. A record of all discussions, decisions, and actions taken must be recorded in the Investigator Site File.

The CI or delegate will inform the Sponsor within 24 hours to discuss the hazard and any actions taken (prior to implementation if time allows). USMs identified shall take immediate effect and the CI or Sponsor will telephone the REC and MHRA ideally within 24 hours (no later than 3 days) to discuss the event with a medical assessor. The CI, Sponsor (or delegate) will further notify the REC and MHRA in writing within 3 days from the date the measures were taken.

If the CI and the Sponsor consider the USM to affect all participants, ExeCTU will inform all PIs of the USM under the CIs oversight.

#### 9.9. The type and duration of the follow-up of participants after adverse reactions.

All SAEs/SARs/SUSARs are followed up until the final outcome is reached or up to the end of the study visit at week 35. Participants should be monitored as per local standard of care practice and treatment should be supportive and guided by symptoms.

#### 9.10. Development safety update reports

A DSUR will be provided to the MHRA and REC by ExeCTU at the end of each reporting year. The CI (or designated representative) in collaboration with ExeCTU will prepare all relevant information for the DSUR. The Sponsor will review the DSUR prior to submission and the CI will review the clinical sections and provide final sign off prior to submission.

#### **10. STATISTICS AND DATA ANALYSIS**

#### 10.1. Target sample size

The target is 222 randomised participants. The sample size calculation is based on a group sequential design with one interim analysis (i.e. total of two looks including the final analysis), using the O'Brien-Fleming spending function. The trial is powered at 90% to detect a between-group difference in change in absolute FVC between baseline and 26 weeks post-randomisation of 58ml, at the 5% two-sided significance level, conservatively assuming a standard deviation (SD) of change in absolute FVC between baseline and 26 weeks post-randomisation of 125ml and allowing for 10% loss-to-follow-up. The target difference is therefore equivalent to a standardised effect size of 0.464. This target difference was informed from data from the INBUILD trial as well as other published trials of fibrosing lung disease (CAPACITY, INPULSIS and ASCEND) [27-30]. The target difference was discussed and agreed with clinicians taking part in the trial and patient representatives. See Appendix 1 for power scenarios based on the planned recruitment target.

There is a planned review (at the time of the interim analysis) of the pooled standard deviation of change in absolute FVC between baseline and week 26, with a blinded sample size reestimation undertaken if indicated. If the observed pooled SD is larger than expected, implications on the required sample size will be discussed, taking into account other factors such as the emerging retention rate at the primary endpoint and rates of completeness of the primary outcome, and remedial action will be considered if deemed necessary.

#### 10.2. Planned recruitment rate

The target is 222 participants randomised over a 25-month recruitment period. The projected mean randomised rate/site/month is ~0.4 participants. The projected recruitment period (25 months) allows for staggered opening of the estimated 30 sites required, with the initial focus on opening 10-15 sites during the first 12 months of the recruitment period as part of the internal pilot phase. The recruitment/randomisation rate will be regularly reviewed by the TMG and trial oversight committees; additional sites may be sought if the recruitment rate is lower than predicted.

#### 10.3. Statistical considerations and statistical analysis plan

A detailed statistical analysis plan (SAP) [31] will be drafted by the trial statisticians, which will be reviewed and approved by an independent statistician prior to database lock. The planned statistical analyses will consider the ICH E9 guideline together with the more recent ICH E9 (R1) addendum on estimands [32]. The primary analyses will be conducted following the collection of the final follow-up data for the last participant, final data cleaning and database lock and data export to the trial statisticians.

Primary analyses of the primary and secondary outcomes will follow the treatment policy approach. Throughout the analysis, emphasis will be placed on estimation and betweengroup comparisons will be presented with two-sided 95% confidence/credible intervals, for both primary and secondary outcomes. Where hypothesis tests are carried out, the statistical significance level will be two-sided at the 5% level. Primary analyses for the primary and secondary outcomes will be adjusted for baseline measures relevant to the outcome under consideration. For completeness, simple unadjusted analyses will also be presented. No adjustments for multiple analyses will be made as the trial has a clearly specified primary outcome. Model assumptions will be visually checked, and bootstrapping implemented as required e.g. to handle substantial deviations from normality. The trial will be reported following the relevant Consolidated Standards Of Reporting Trials (CONSORT) guidelines [33, 34] and relevant extensions, including for Pragmatic Trials; Patient Reported Outcomes.

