#### 10.6. Primary analysis of the primary outcome

The primary outcome in this trial is change in absolute FVC between baseline and 26 weeks post-randomisation. The primary analysis of the primary outcome will compare change in absolute FVC between allocated groups using a repeated measures (longitudinal) mixed-effects model to facilitate inclusion of participants who provide at least one post-baseline FVC (12 and/or 26 weeks), maximising use of available FVC data and minimising effects of loss-to-follow-up. This will model change in FVC at 12 weeks (i.e. baseline minus 12 weeks) and 26 weeks (i.e. baseline minus 26 weeks) via the inclusion of allocated treatment-by-time interaction terms, adjusting for pre-specified baseline variables (including baseline FVC) and site as a random effect.

The estimated between-group difference in change in absolute FVC at 26 weeks will be extracted from this model, together with confidence interval, to obtain the primary result of the primary analysis.

It is noted that modelling absolute FVC at 26 weeks as the primary outcome, with adjustment for baseline absolute FVC, would give the same estimated treatment effect as modelling the change in FVC between baseline and 26 weeks (with adjustment in the model for baseline FVC). However, defining the primary outcome as change in absolute FVC was chosen on the basis of easier interpretation, as change in FVC is commonly used when discussing disease progression with patients and is also used in the majority of trials/research in this field.

Potential key intercurrent events (e.g. treatment discontinuation/withdrawal, death) will be considered, with the primary analysis using a treatment policy strategy i.e., all participants will be analysed according to the group they were allocated. This is line with the primary aim of the trial, which is to assess the effectiveness of prednisolone, in comparison with placebo, regardless of compliance with allocated treatment, therefore the primary analysis will be programmed and undertaken following the intention-to-treat principle.

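### Section 10.3 sets 5% for every test with no adjustment for multiple analyses, which conflicts with the two-look O'Brien-Fleming design in 10.1 and 10.12

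*Protocol*

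**What the plan says.** Two parts of the protocol bear on the level of the final primary test.

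**The design sections.** Section 10.1: "The sample size calculation is based on a group sequential design with one interim analysis", with two looks in total and an O'Brien-Fleming spending function. The level for that design is given as "at the 5% two-sided significance level". Section 10.12 uses the same function to determine the boundaries and places the interim when the first 100 randomised participants reach week 26. Section 4.2 describes this look as an interim analysis for effectiveness.

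**The general analysis section.** Section 10.3: "Where hypothesis tests are carried out, the statistical significance level will be two-sided at the 5% level". The same section sets two-sided 95% intervals for primary and secondary outcomes, and then states: "No adjustments for multiple analyses will be made as the trial has a clearly specified primary outcome". No clause excepts the primary outcome at the final analysis. Section 10.6 says that the week-26 difference "will be extracted from this model, together with confidence interval, to obtain the primary result of the primary analysis", without saying at what level that interval is set.

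Neither part gives a numerical boundary for either look. Section 10.12 leaves the details of the interim to the SAP or a separate interim analysis plan, neither of which is at hand.

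**The concern.** A spending function divides one overall alpha between the looks. Once some is used at an interim that can declare effectiveness, the final look has less than 5% left. Section 10.3 assigns 5% to every test and 95% to the primary interval, so read literally it gives the final primary test the full 5% as well.

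The reason 10.3 offers for making no adjustment is that there is one clearly specified primary outcome. That answers multiplicity across outcomes. It does not answer two looks at the same outcome. Because the sentence speaks of analyses rather than outcomes, a reader can take it to cover the interim look too.

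What is at stake is a narrow band of final p-values just under 0.05, where the trial would be positive under one section and not under the other. The reported 95% interval could likewise exclude zero while the group-sequential boundary is not crossed. This should be settled before any unblinded comparison is made.

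**Working it through.** **Inputs**
- Section 10.1: target difference 58 ml, SD 125 ml, 90% power, two-sided 5%, 10% loss to follow-up, 222 randomised, two looks.
- Section 10.12: interim when the first 100 randomised reach week 26.
- Section 4: 1:1 allocation.
- Assumption: information fraction t. The protocol gives no value. 100/222 = 0.45 and 90/200 evaluable = 0.45; 100/200 = 0.50. The range used is 0.45 to 0.50.
- Assumption: form of the spending function. The protocol does not say whether it is applied to the two-sided 5% or to 2.5% in each tail. Both are shown, with the classical O'Brien-Fleming boundary for comparison.

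**Step 1. The plan's sample size.** The fixed-design normal formula gives n per arm = 2 × (1.960 + 1.282)² × (125/58)² = 97.6, so 98. Then 98/0.9 = 108.9, so 109 per arm and 218 in total, within 2% of 222. With the t distribution, 99 per arm are needed. The group-sequential inflation of 1.002 to 1.008 brings this to just under 100, and 200/0.9 = 222. The stated target is therefore reproduced as a two-look design with 5% as the overall level.

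**Step 2. Alpha spent at the interim.**
- Two-sided form: α₁ = 2[1 − Φ(1.960/√t)]. At t = 0.45 this is 2[1 − Φ(2.922)] = 0.0035; at t = 0.50 it is 2[1 − Φ(2.772)] = 0.0056.
- Per-tail form: α₁ = 4[1 − Φ(2.241/√t)]. This is 0.0017 at t = 0.45 and 0.0031 at t = 0.50.

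**Step 3. Final boundary and overall error.** The two test statistics are bivariate normal with correlation √t. The correct final value c₂ solves P(|Z₁| ≥ c₁ or |Z₂| ≥ c₂) = 0.05 under no effect. Replacing c₂ by 1.960 gives the overall error if 10.3 is followed literally. Power is at 58 ml with 99.9 evaluable per arm (222 × 0.9 / 2).

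| Form | t | c₁ | c₂ | Final nominal p | Overall alpha if final test uses 1.960 | Power with c₂ | Power with 1.960 |
|---|---|---|---|---|---|---|---|
| Two-sided | 0.45 | 2.922 | 1.972 | 0.0486 | 5.14% | 0.9051 | 0.9071 |
| Two-sided | 0.50 | 2.772 | 1.979 | 0.0478 | 5.22% | 0.9043 | 0.9075 |
| Per tail | 0.45 | 3.144 | 1.965 | 0.0494 | 5.06% | 0.9059 | 0.9067 |
| Per tail | 0.50 | 2.963 | 1.969 | 0.0490 | 5.10% | 0.9055 | 0.9070 |

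The classical boundary at t = 0.50 has c₂ = 1.977, final p 0.0480 and overall alpha 5.20%, inside the same range.

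**Step 4. Size.**
- Excess type I error: 0.06 to 0.22 percentage points.
- Interval half-width: 1.965/1.960 = 1.003 to 1.979/1.960 = 1.010, so at most about 1% wider. The matching interval level is 95.06% to 95.22%.
- Power given up by using c₂: 0.9067 − 0.9059 = 0.0008 to 0.9075 − 0.9043 = 0.0032.

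**The case against.** The strongest reply is that the adjustment is already in the protocol. Section 10.1 attaches 5% to the whole two-look design, as does Appendix 1, and a spending function by definition leaves a reduced final boundary. Section 10.12 takes the boundaries from it. Specific group-sequential provisions would normally govern a general sentence on significance levels, and the no-adjustment sentence gives a reason that concerns outcomes only. This stands as far as it goes. A reader might infer from 10.3 that the final test is fixed at an unadjusted 5%, or that the trial's type I error does exceed 5%. The protocol does not support either inference, because 10.1 and 10.12 point the other way.

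A reader might also object that the protocol prescribes no correction of the estimate or interval after an early stop. That is not a finding here: section 10.12 defers interim details to the SAP or an interim analysis plan, and such corrections commonly belong there.

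The reply does not remove the conflict. The final significance level and the interval level are not deferred. Section 10.3 states them without exception, and someone drafting the SAP from that section could follow it as written. If 10.12 implies a lower final level, that confirms the two sections disagree.

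**Conclusion.** The point holds as an internal inconsistency, small in effect. Section 10.3 gives one rule for the level of the final primary test and 10.1 with 10.12 imply another. The consequence is confined to final p-values between about 0.0478 to 0.0494 and 0.05. Under the literal reading of 10.3, overall two-sided error would be about 5.06% to 5.22%. That figure is conditional: it applies only if the boundaries in 10.1 and 10.12 are not carried to the final test.

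The numbers rest on an information fraction of 0.45 to 0.50, on the form of the spending function, and on an interim that can declare effectiveness. Sections 4.2 and 10.1 support the last assumption, although the decision wording in 10.12 speaks of continuing when there is evidence of activity and does not spell out an efficacy stop.

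**What to change.** In section 10.3:
- State that two-sided 5% is the overall level for the primary outcome across the interim and final looks.
- State that the final primary test and its interval use the level left by the O'Brien-Fleming spending function, recomputed from the information actually used at the interim.
- Limit the sentence on making no adjustments for multiple analyses to secondary outcomes.

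A cross-reference in section 10.6 would tie the reported primary interval to the same level.

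The cost is a few sentences. The target of 222 is unchanged, and power at the adjusted level is about 90.4% to 90.6%, a loss of at most about 0.3 percentage points against an unadjusted final test.

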#### **10.4. Participant analysis populations**

The primary analysis population will include all participants as randomised (i.e. treatment policy strategy), who provide at least one post-baseline FVC measure: the primary analyses will include observed data in repeated measures models, allowing the inclusion of all participants who provide at least one post-baseline FVC measure. Primary analyses of secondary outcomes will similarly follow a treatment policy strategy.

Secondary analyses of the primary outcome will consider adherence with allocated treatment, i.e., based on participants who meet a minimum threshold of participant reported selfadherence with their allocated trial treatment; full details will be included in the SAP.

The secondary outcomes relating to safety (related adverse events, serious adverse events) will be considered on an as treated basis.

#### 10.5. Summary of baseline data and flow of participants through the trial

Baseline characteristics of participants will be summarised descriptively by allocated group and used to assess for any marked baseline differences in demographics or outcome measures between the two allocated groups. Loss to follow-up after randomisation will be reported separately for each group, summarised visually via a CONSORT flow diagram. Baseline characteristics will be subjectively examined to assess for potential differences between participants who withdraw, discontinue treatment, and those who complete the trial.

#### 10.6. Primary analysis of the primary outcome

The primary outcome in this trial is change in absolute FVC between baseline and 26 weeks post-randomisation. The primary analysis of the primary outcome will compare change in absolute FVC between allocated groups using a repeated measures (longitudinal) mixed-effects model to facilitate inclusion of participants who provide at least one post-baseline FVC (12 and/or 26 weeks), maximising use of available FVC data and minimising effects of loss-to-follow-up. This will model change in FVC at 12 weeks (i.e. baseline minus 12 weeks) and 26 weeks (i.e. baseline minus 26 weeks) via the inclusion of allocated treatment-by-time interaction terms, adjusting for pre-specified baseline variables (including baseline FVC) and site as a random effect.

The estimated between-group difference in change in absolute FVC at 26 weeks will be extracted from this model, together with confidence interval, to obtain the primary result of the primary analysis.

It is noted that modelling absolute FVC at 26 weeks as the primary outcome, with adjustment for baseline absolute FVC, would give the same estimated treatment effect as modelling the change in FVC between baseline and 26 weeks (with adjustment in the model for baseline FVC). However, defining the primary outcome as change in absolute FVC was chosen on the basis of easier interpretation, as change in FVC is commonly used when discussing disease progression with patients and is also used in the majority of trials/research in this field.

Potential key intercurrent events (e.g. treatment discontinuation/withdrawal, death) will be considered, with the primary analysis using a treatment policy strategy i.e., all participants will be analysed according to the group they were allocated. This is line with the primary aim of the trial, which is to assess the effectiveness of prednisolone, in comparison with placebo, regardless of compliance with allocated treatment, therefore the primary analysis will be programmed and undertaken following the intention-to-treat principle.

#### 10.7. Handling of intercurrent events in primary estimand

Intercurrent events related to adherence to treatment (i.e. discontinuation/withdrawal) will be handled using the treatment policy strategy; the treatment effect is estimated irrespective of the occurrence of such an intercurrent event. This policy is in alignment with an intention-to-treat analysis. Deaths during the trial will be handled using the "while alive" approach; participant data collected prior to death will be included in the analyses.

# 10.8. Sensitivity, subgroup and additional analyses of the primary outcome

Sensitivity, supporting and subgroup (e.g. subgroup of participants with clearly documented environmental exposure causing FHP) analyses of the primary outcome will be pre-specified in the detailed statistical analysis plan.

A linear mixed model will be used to combine all the post-randomisation absolute FVC results into a single model which will adjust for the same factors as the primary analysis of the primary outcome and include a participant identifier as a random effect. An interaction between allocated group and time will also be included to assess if any effect of prednisolone is constant over time or varies as time progresses.

The pattern of missing data will be assessed and if appropriate, a sensitivity analysis will use multiple imputation to account for missing primary outcome data under the assumption that the data are missing at random. If the data are not considered missing at random, then a sensitivity analysis of the results will be undertaken by considering appropriate scenarios, such as worst-case scenario or pattern-mixture models.

With regards to capturing/assessing adherence, pill counts would not be viable due to participants being able to escalate the dose and risks of unblinding. Whilst participants will be asked to report their adherence to treatment, experience suggests that such data might not be complete or reliable. However, if sufficient numbers of participants self-report adherence/non-adherence, a complier average causal effect (CACE) analysis will be undertaken.

# 10.9. Adjusted analysis

Additional adjusted analysis may be undertaken including baseline factors found to be unbalanced between allocated at baseline and thought to be predictive of the primary outcome.

#### 10.10. Primary analysis of secondary outcomes

Secondary outcomes will be reported descriptively at each timepoint collected. Analysis of secondary outcomes, including the PROMS, will use similar mixed-effects models, with adjustments for baseline outcome where relevant, maximising the use of longitudinal data where possible. Binary outcomes (initiation of anti-fibrotic medication/additional immunosuppressive therapy; hospitalisations/acute exacerbations/death) will be analysed using logistic regression and time to event analyses, with adjustments in the models as per the primary analyses. Secondary outcomes assessing safety, such as related adverse events and serious adverse events, will be descriptively summarised only.

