## 3.2. Secondary objectives

- Assess effectiveness of prednisolone vs placebo on disease progression at 12 weeks post-randomisation on FVC
- Assess effectiveness of prednisolone vs placebo on disease progression at 26 weeks post-randomisation on (a) FVC, (b) Diffusion Co-efficient for carbon monoxide (DLco)
- Assess initiation of antifibrotic therapy and/or additional immunosuppressive therapy during the 26-week treatment period
- Assess effect of prednisolone vs placebo on participant-reported outcome measures (PROMs) of quality of life, including disease-specific quality of life measures, at baseline, week 12 and week 26 post-randomisation

- Assess safety of prednisolone
- Assess health/social care service resource use
- Assess cost-effectiveness of prednisolone vs placebo over 26 weeks of treatment

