#### 3.3.2. Secondary outcomes

- Absolute FVC, measured in millilitres (ml) will be recorded using the pulmonary function test (PFT) at 12 weeks post-randomisation, and used to calculate change in absolute FVC between baseline and 12-weeks post-randomisation.
- 2. Percentage change in FVC will be calculated (using the absolute FVC values collected at baseline, 12 and 26 weeks post-randomisation) between (i) baseline and 12 weeks and (ii) baseline and 26 weeks post-randomisation.
- Absolute change in percentage predicted FVC will be calculated between (i) baseline and 12 weeks and (ii) baseline and 26 weeks post-randomisation, using percentage predicted FVC calculated centrally by ExeCTU using Global Lung Initiative (GLI) reference equation.
- 4. Absolute DLco, measured in mmol min kPa, will be recorded using the European Respiratory Society (ERS) guidelines, at baseline and 26-weeks post-randomisation and used to calculate change in absolute DLco between baseline and 26 weeks post-randomisation.
- 5. Percentage change in DLco will be calculated (using the absolute DLco values collected at baseline and 26 weeks post-randomisation) between baseline and 26 weeks post-randomisation.
- 6. Absolute change in percentage predicted DLco will be calculated between baseline and 26 weeks post-randomisation.
- 7. Initiation of antifibrotic therapy given by 26 weeks post randomisation.
- 8. Additional immunosuppressant therapy given by 26-weeks post-randomisation.
- 9. Quality of life will be measured at baseline, 12 and 26 weeks post-randomisation. Changes in quality of life from (i) baseline to week 12 and (ii) baseline to week 26 will be measured using
  - L-PF questionnaire [22] (dyspnoea, cough and fatigue domain scores of principal interest)
  - PGI-S scale [23]
  - the cough VAS [24]
  - EQ-5D-5L Visual Analogue Scale [25]
- 10. Safety data will be collected in accordance with MedDRA and defined as the number and proportion of participants experiencing Serious Adverse Events (SAEs) and

related Adverse Events (AEs) throughout the duration of the trial. Specific events of interest are:

- o adverse reactions
- o respiratory hospitalisations
- o acute exacerbations
- weight gain/increased waist circumference (percentage change)
- o adverse events of special interest- infections (listed in section 9.3)
- o death

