#### 9.3. Recording and reporting of Adverse events (AEs)

The safety reporting period will begin from the time of randomisation up to the week 35, End of Study telephone follow-up. The recording and reporting requirements are summarised in the safety reporting flowchart in Figure 5. Adverse events should be reviewed at every follow up visit.

Figure 5: Safety reporting flow chart

All adverse events will be assessed for seriousness and causality as per the definitions in section 9.1 above. These assessments should be carried out by the site PI, or delegated medically qualified doctor, and recorded in the medical notes. If the adverse event is possibly, probably or definitely related to prednisolone it is considered an adverse reaction (AR) and must be reported in the adverse event eCRF in REDCap. In addition to this any viral, fungal or bacterial infections of any kind are considered Adverse Events of Special Interest (AESI) for this trial and must be reported on the adverse event eCRF. If the adverse event doesn't meet the definition of serious and is not considered to be an AESI or AR it should only be documented in the participants medical notes but not be reported on the adverse event eCRF.

All related and unrelated adverse events that are considered serious, as defined in section 9.1, must be reported as an SAE. Additional guidance for reporting serious adverse events can be found in section 9.4 below.

As this is a blinded trial, adverse events should be evaluated on the assumption that the participant was allocated the active drug i.e. prednisolone. The blind should only be broken where knowing the allocation is clearly necessary and will alter the appropriate medical management of the participant. If unblinding is necessary, please refer to the Emergency Unblinding section of the protocol (7.7.1) and the CHORUS 'Unblinding' working instruction.

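### Low-cost improvement: section 10.10 models hospitalisations, exacerbations and death but, read naturally, leaves infections, the only named AESI, without a between-group estimate

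*Protocol*

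**What the plan says.** Protocol section 3.2 lists "Assess safety of prednisolone" among the secondary objectives. Within safety outcome 10, section 3.3.2 names specific events of interest: adverse reactions, respiratory hospitalisations, acute exacerbations, weight or waist gain, death, and "adverse events of special interest- infections (listed in section 9.3". Section 9.3 states that "any viral, fungal or bacterial infections of any kind are considered Adverse Events of Special Interest (AESI) for this trial", and requires each one on the adverse event eCRF. Other events that are neither serious nor related stay in the medical notes.

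Section 10.10 divides the event outcomes in two. One group is modelled: starting antifibrotic or further immunosuppressive treatment, and "hospitalisations/acute exacerbations/death) will be analysed using logistic regression and time to event analyses". For the rest: "Secondary outcomes assessing safety, such as related adverse events and serious adverse events, will be descriptively summarised only".

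Three other statements bear on the point:
- Section 10.3: between-group "comparisons will be presented with two-sided 95% confidence/credible intervals, for both primary and secondary outcomes".
- Section 10.4: "The secondary outcomes relating to safety (related adverse events, serious adverse events) will be considered on an as treated basis".
- Section 9.3: "The safety reporting period will begin from the time of randomisation up to the week 35, End of Study telephone follow-up". Section 3.3.2 likewise defines outcome 10 over the whole trial.

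**The concern.** Infection is the one harm that the protocol names as an AESI and collects in full, whatever its seriousness or cause. Three other events of interest from the same list (respiratory hospitalisations, exacerbations, death) are moved up to a modelled comparison. Infections are not, and the wording of 10.10 places them with the outcomes that are only described.

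A reader weighing an FVC benefit of prednisolone against its harms would then have per-arm infection counts but no planned contrast with its uncertainty. That is a weaker choice than the data allow for the safety objective. The primary result, the sample size and the safety counts themselves are unaffected.

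**Working it through.** **1. Where infections fall.**

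| Event of interest (3.3.2, outcome 10) | Treatment in 10.10 |
|---|---|
| Respiratory hospitalisations | modelled (as hospitalisations) |
| Acute exacerbations | modelled |
| Death | modelled |
| Adverse reactions | descriptive (related adverse events are a named example) |
| Infections (AESI) | not named; a safety outcome, so descriptive on the natural reading |

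The examples in the descriptive sentence are introduced by *such as*, so the sentence reaches beyond related and serious events. The modelled list carries no such opening. The general rule on intervals in 10.3 points the other way, but the specific rule in 10.10 would normally prevail.

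**2. What is already fixed.** The analysis set is as treated for safety outcomes (10.4). The two examples in brackets there do not include a non-serious, unrelated infection, but infections belong to the safety outcome, so little inference is needed. The window is randomisation to week 35 (3.3.2, 9.3). Outcome 10 is expressed as a number and proportion of participants. What is missing is the between-group contrast and its interval.

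**3. How precise the contrast would be.** The protocol has no figure for infections to reproduce and gives no rates, so all counts below are assumptions. The size per arm follows from section 10.1 and 1:1 allocation: 222/2 = 111, or 100 after 10% loss (111 × 0.9 = 99.9).

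Newcombe interval for d = p1 − p0 (prednisolone minus placebo), with Wilson limits (l, u) for each arm:
- lower = d − √[(p1 − l1)² + (u0 − p0)²]
- upper = d + √[(u1 − p1)² + (p0 − l0)²]

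Example, 22/111 v 39/111: p0 = 19.82% (13.47 to 28.19), p1 = 35.14% (26.89 to 44.38), d = 15.32 points.
- lower = 15.32 − √(8.25² + 8.37²) = 3.6
- upper = 15.32 + √(9.24² + 6.35²) = 26.5

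| Placebo v prednisolone, participants with at least one infection | n per arm | Risk difference, points (95% CI) | Half-width |
|---|---|---|---|
| 6 v 11 | 111 | 4.5 (−2.8 to 12.1) | 7.4 |
| 11 v 22 | 111 | 9.9 (0.5 to 19.3) | 9.4 |
| 22 v 22 | 111 | 0 (−10.5 to 10.5) | 10.5 |
| 22 v 33 | 111 | 9.9 (−1.5 to 21.0) | 11.2 |
| 22 v 39 | 111 | 15.3 (3.6 to 26.5) | 11.5 |
| 33 v 50 | 111 | 15.3 (2.6 to 27.4) | 12.4 |
| 20 v 35 | 100 | 15.0 (2.6 to 26.8) | 12.1 |

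Check by the Wald formula, half-width = 1.96 √[p0(1−p0)/n + p1(1−p1)/n], n = 111:
- 20% v 30%: 1.96 √[(0.16 + 0.21)/111] = 11.3 points
- 40% v 50%: 1.96 √[(0.24 + 0.25)/111] = 13.0 points

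The half-width is therefore about 7 to 13 points over these assumptions.

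**4. Why a 26-week version is useful support.** From the dosing table in section 8.6.1:
- Days 0–181: 40×14 + 30×28 + 20×28 + 10×14 + 10×98 = 3080 mg; 3080/182 = 16.9 mg/day.
- Days 182–245 (wean): 5×7 + 4×14 + 3×14 + 2×14 + 1×15 = 176 mg; 176/64 = 2.75 mg/day.
- Share in the first 26 weeks: 3080/3256 = 94.6%.

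These are planned doses only. Section 8.7 recommends a short escalation for intercurrent infections, so the dose taken can follow an infection. This supports a secondary window, not replacement of the protocol's own.

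**The case against.** The case for leaving the text alone is reasonable. Descriptive safety reporting is normal, and adverse reactions, also an event of interest, are descriptive too. Infections are not named in 10.10, and the SAP, approved by an independent statistician before database lock, could add an infection contrast with support from 10.3. Serious infections may partly appear among hospitalisations, and the DMC sees unblinded safety data by group. An imprecise interval might also be misread as reassurance: for 20% v 30% with 111 per arm, power is only 0.40.

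Most of this stands, and it keeps the point optional. It does not remove it. Restricting these outcomes to description is a choice stated in the protocol, not a detail left open for the SAP. Neither hospitalisations nor DMC monitoring yields an infection estimate in the final analysis. An interval also shows the imprecision that bare counts hide.

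A reader might infer more than the documents support:
- *That the analysis set and window for infections are open.* Sections 10.4, 3.3.2 and 9.3 effectively set them: as treated, randomisation to week 35. Making as-randomised or 26 weeks the main analysis would conflict with those sections.
- *That any infection comparison must be chosen after unblinding or left to the reader.* The SAP can still fix one in advance.
- *That 10.3 and 10.10 flatly contradict each other.* A specific rule can limit a general one, and 10.3 governs how comparisons are shown, not which are made.

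**Conclusion.** The point holds as a low-cost improvement, not an error. On the natural reading of 10.10, the only named AESI has no planned between-group estimate, while three neighbouring events of interest do. Nothing in the primary analysis, sample size or safety counts is wrong, and a reader could form a crude interval from per-arm counts. The gain is a planned estimate for the harm that the protocol itself puts first. With 111 per arm its half-width would be about 7 to 13 points. That range rests wholly on assumed infection proportions (about 5% to 50% per arm), because the protocol gives none. Only a large excess would be clearly separated from zero.

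**What to change.** Add to section 10.10 that the proportion of participants with at least one AESI infection will also be compared between groups as a risk difference with a two-sided 95% CI, presented as an estimate and not a test. Keep the protocol's existing basis: as treated (10.4), from randomisation to week 35 (3.3.2, 9.3). Give as-randomised and 26-week versions as supportive analyses. Leave the other adverse event and SAE categories, and infection recurrence and severity, descriptive.

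The cost is a sentence or two and a short analysis of data already collected; there are no new visits, tests or participants. The downsides are one more imprecise secondary contrast without multiplicity adjustment, in line with 10.3, and a measure that ignores repeat and more severe infections.
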